Trial design: Open label, single cohort proof of concept trial. An additional arm of the study will be for subjects treated with the study drug in malignant pituitary tumors. Three clinical trial sites, one at CSMC and the others at Johns Hopkins Hospital and Massachusetts General Hospital.

Study population: Patients will be recruited from the Pituitary Center at Cedars-Sinai Medical Center and the other two sites.

Intervention: lapatinib 1250 mg daily for 6 months. Patients will be treated with the standardized dose used in breast cancer therapy for six months (Cameron & Stein 2008; Geyer et al. 2006). The drug will be supplied by Novartis Oncology.

- a. Primary outcome variable.

Primary outcome in nonfunctioning pituitary adenomas: 40% reduction in tumor size in any dimension. Tumor size and volume will be calculated using Open Source OsiriX® Imaging Software for MacOS. MRIs will be performed at baseline and at 3 and 6 months All MRIs will be centrally read by the dedicated pituitary radiologist at CSMC.

Primary outcome in prolactinomas: 40% reduction in tumor size in any dimension.

Primary outcome in malignant pituitary tumors: Progression free survival

- b. Secondary outcome variables.

Secondary outcomes in prolactinomas:

(a) achievement of 50% reduction of PRL levels (b) PRL normalization (c) percent reduction in PRL levels (d) percent reduction in tumor volume. Tumor volume will be calculated using Open Source OsiriX® Imaging Software for MacOS. (e) correlation of tumor size and PRL reduction (f) clinical predictors of TKI response, including age, gender, duration of disease, dose and duration of dopamine agonist therapy, baseline PRL, and baseline tumor size.

Secondary outcomes in malignant pituitary tumors: partial response, complete response, mortality, 24 hour urine free cortisol levels for Cushing carcinomas, IGF-1 levels for acromegaly carcinomas.

We will correlate ErbB receptor expression with the subjects' clinical response to the study drug. This will be performed through immunohistochemistry staining of pituitary tumor slides from surgery.

Section 5.0. Selection and Withdrawal of Subjects

Inclusion criteria: Subjects with non-functioning pituitary adenomas, who have undergone at least one prior surgical resection and have demonstrated recurrence on MRI.

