Subjects with prolactinomas who are resistant to dopamine agonist therapy who manifest continued tumor size growth while on a dopamine agonist, unless intolerant of adequate doses of a dopamine agonist.

Subjects with malignant pituitary tumors will be eligible for the malignant pituitary tumor arm of the study regardless of existing visual deficits.

Exclusion criteria: Children will be excluded. If subjects have preexisting visual field deficits, they will be monitored on more frequent basis. Patients will also be excluded if they have left ventricular ejection fraction less than 50 %, moderate to severe hepatic impairment (see below for specifics), active hepatitis, HIV positivity, concurrent cancers, life expectancy less than one year, and pregnancy. Pregnant patients will be excluded. Childbearing age women will be required to use

contraception. Patients who become pregnant during the study should discontinue the study immediately.

Withdrawal of Subjects:

Monitoring for adverse effects: Prior to initiating therapy, patients will undergo an echocardiogram and ECG to evaluate the ejection fraction, and the echocardiogram will be repeated every 8 weeks (Visit 3, 5, and 7) and on visit 8. Patients will also undergo ophthalmic testing at visits 1, 4, and 7. Patients with pre-existing stable visual field compromise prior to enrollment will undergo visual field testing at visits 1, 2, and 3, and if stable, then they will proceed with visual field testing every three months for the duration of the study. Patients will be evaluated for adverse effects monthly with physical examinations, chemistry and hematology panels, and ECGs. Adverse events will be graded by the NCI-CTC and include: anorexia, decreased ejection fraction, interstitial lung disease/pneumonitis, diarrhea, nausea, vomiting, hepatotoxicity, rash, and fatigue. Lapatinib will be discontinued in those who developed decreased ejection fraction, who develop pulmonary symptoms, retinal toxicity, worsening of visual fields, and those with toxicity greater than or equal to Grade 2 on the NCI-CTC. [name], from Oncology department at Cedars-Sinai Medical Center, will assist us in monitoring patients for adverse events.

If at any time a patient demonstrates compromise of his visual fields, dilated retinal exam or tumor growth on MRI, he will be withdrawn from the study and referred for surgery.

Section 6.0 Treatment of Subjects

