Pregnancy Test for pre-menopausal women	X	X	X	X	X	X	X	X

^ Only for subjects with visual field deficits

^^ will be waived if subjects had MRI at outside hospital within 3 months of baseline visit

* Only for subjects with acromegaly from malignant tumors

+Only for subjects with ACTH secreting adenomas from malignant tumors

**Visit 8 is only required if stopping Lapatinib at visit 7. Patients continuing on Lapatinib after visit 7 will be followed by their physician as clinically appropriate.

Section 7.0 Assessment of Efficacy

a. Primary outcome variable.

Primary outcome in nonfunctioning pituitary adenomas: 40% reduction in tumor size in any dimension. Tumor size and volume will be calculated using Open Source OsiriX® Imaging Software for MacOS. MRIs will be performed at baseline and at 3 and 6 months All MRIs will be centrally read by the dedicated pituitary radiologist at CSMC.

Primary outcome in prolactinomas: 40% reduction in tumor size in any dimension.

Primary outcome in malignant pituitary tumors: Progression free survival

b. Secondary outcome variables.

Secondary outcomes in prolactinomas:

(a) achievement of 50% reduction of PRL levels (b) PRL normalization (c) percent reduction in PRL levels (d) percent reduction in tumor volume. Tumor volume will be calculated using Open Source OsiriX® Imaging Software for MacOS. (e) correlation of tumor size and PRL reduction (f) clinical predictors of TKI response, including age, gender, duration of disease, dose and duration of dopamine agonist therapy, baseline PRL, and baseline tumor size.

Secondary outcomes in malignant pituitary tumors: partial response, complete response, mortality, 24 hour urine free cortisol levels for Cushing carcinomas, IGF-1 levels for acromegaly carcinomas

We will correlate ErbB receptor expression with the subjects' clinical response to the study drug. This will be performed through immunohistochemistry staining of pituitary tumor slides from surgery.

Section 8.0 Assessment of Safety

1. *Monitoring for adverse effects (further detailed below):* Data has been collected on over 12000 subjects on combination therapy of lapatinib and other chemotherapies, and over 4000 subjects have been treated with lapatinib monotherapy, with 2347 of those specifically in breast cancer. With monotherapy, majority of AEs were Grade 1 or 2 in severity. The incidence of Grade 3 and Grade 4 events was 21% in those

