who received lapatinib and 7% in those on placebo. Risks of adverse events are not additive or cumulative. SAEs were reported in 6% of those on lapatinib compared to 5% on placebo. Cardiac events including left ventricular ejection fraction decreases were reported in approximately 1% of patients and most have partial or full recovery. Symptomatic decreases in ejection fraction were observed in approximately 0.3% of patients on lapatinib. Interstitial lung disease is observed in 0.2% of patients. Hepatotoxicity has been observed in <1% of patients. Grade 3 and 4 diarrhea occurs in <10% of patients. Nausea may be seen in 18% of patients and rash in 29% (Investigators' Brochure).

2. Prior to initiating therapy, patients will undergo an echocardiogram and ECG to evaluate the ejection fraction, and the echocardiogram will be repeated every 8 weeks and on visit. Patients will be evaluated for adverse effects monthly with physical examinations, chemistry and hematology panels, and ECGs. Adverse events will be graded by the NCI-CTC. Common adverse events include: hand-foot syndrome, rash, diarrhea, indigestion, nausea, vomiting, anorexia, anemia, low platelets, abnormal liver tests (ALT (SGPT) level raised, AST/SGOT level raised, hyperbilirubinemia, backache, pain in limb, insomnia, fatigue, and shortness of breath. Rare but serious events include: heart failure (depression of left ventricular systolic function), abnormal heart beat (prolonged QT interval), liver damage (hepatotoxicity), and lung problems (interstitial lung disease/pneumonitis). Lapatinib will be discontinued in those who developed decreased ejection fraction, who develop pulmonary symptoms. Those subjects with toxicity less than or equal to Grade 2 on the NCI-CTC will have their dose held and resumed when the toxicity has resolved. Those subjects with toxicity equal to Grade 3 on the NCI-CTC will have their dose held and resumed at a fifty percent dose reduction when the toxicity has resolved. Those subjects with toxicity equal to Grade 4 on the NCI-CTC will be discontinued on the study drug. [name], from Oncology department at Cedars-Sinai Medical Center, will assist us in monitoring patients for adverse events.
3. If at any time a patient demonstrates a worsening of their visual fields or tumor growth on MRI, they will be withdrawn from the study and referred for surgery.

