Patients should be instructed to notify the investigator if it is determined after completion of the study that they become pregnant either during the treatment phase of the study or within five days after the treatment period.

Whenever possible a pregnancy should be followed to term, any premature termination reported, and the status of the mother and child should be reported to GlaxoSmithKline after delivery.

Section 9.0.

Statistics

Sample size calculation for prolactinomas: Sample size was computed using proportions as standard deviation for tumor reduction on the study drug was unknown. While for the data analysis we will use quantitative analysis using the Hotelling’s T², using binary data for power calculations would be inefficient as this would require a larger sample size. We could not use the quantitative analysis for power calculations, however, as we do not know the variance.

The primary outcome is a reduction in maximal size of resistant tumors. Stabilization is defined as <20% reduction in any dimension on MRI by RECIST criteria. MRIs will be performed at baseline and at 3 and 6 months.

The null hypothesis is H₀: no reduction P<0.20 vs. the alternative hypothesis H_a: P>0.40. This will give an effect size of 0.20 to detect. Exact confidence interval and significance test is obtained from the binomial distribution. The reduction is for resistant prolactinomas (Di Sarno, 2001; Delgrange, 2009). Power is >80%, using one tailed

CSMC Office of Research Compliance

Reference: [ICH E6: Good Clinical Practice: Consolidated Guidance](#)

RECOMMENDED ELEMENTS OF A SCIENTIFIC PROTOCOL
(Noted sections should only be included as applicable to your research)

hypothesis, alpha of 0.10. This gives a target sample size of 24 subjects to achieve this power.

Sample size: use one-sided exact test. $H_0: p = p_0$; $H_A: p > p_0$.

Power	alpha	P_0 : null proportion	P_1 : true proportion	N
80%	0.05	20%	30%	116
80%	0.10	20%	30%	88
80%	0.05	20%	35%	56
80%	0.10	20%	35%	44
80%	0.05	20%	40%	35
80%	0.10	20%	40%	24

Secondary MRI studies will deal with various aspects and location by MRI of these tumors. Secondary PRL statistical studies will also be carried out under secondary outcomes.

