Tumor maximal size will be obtained at baseline, 3 months, 6 months after initiation of treatment. The primary hypothesis is the change from baseline to 6 months. The analysis using maximal resistant tumor size will be carried out for the specified times given above. Initially this will be by descriptive analytic and then by inferential analysis using the test for change between baseline and 6 months and change between baseline and 3 months using rank test. We will also use Hotelling's T^2 to combine both pre-post changes.

This study is in the clinical trials paradigm essentially a Phase IIa trial and thus use of alpha type 1 error is at 10%. This is sanctioned by the biostatistics section of NCI.⁴⁰ We will also analyze the secondary endpoints of Aim 1 according to the above models. Concepts behind analysis for quantitative and binary are the same though the methods are different.

Our overall target sample size is 30 subjects which includes nonfunctioning adenomas and prolactinomas, 15 to be recruited from Cedars Sinai Medical Center and 15 from Johns Hopkins Hospital and Massachusetts General Hospital. We aim to recruit 24 subjects with prolactinomas and 6 nonfunctioning adenomas.

Due to the rarity of pituitary tumors in the general population and even more rare are aggressive pituitary tumors such as we propose to study, it is difficult to do a randomized placebo controlled trial with sufficient sample size numbers to achieve adequate power. By using the subjects as their own controls, we alleviate the issues with recruitment. This is a safety and activity trial to look for a sufficient effect of the drug on tumor growth before proceeding to a larger, randomized placebo controlled trial.

Section 10.0. Quality Control and Quality Assurance

Only samples and data collected with appropriate consent will be used for the proposed analysis. Specimens and data collected under the proof of concept clinical trial of lapatinib will be coded in such a way so that other members of the research team will be unable to ascertain the identity of specific patients. All of our data will be

RECOMMENDED ELEMENTS OF A SCIENTIFIC PROTOCOL
(Noted sections should only be included as applicable to your research)

38

maintained confidentially. Data will be kept in locked file cabinets and in password protected files on computer systems.

Section 11.0 Ethical considerations relating to the trial

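### The benign-tumour response rule credits a 40% fall in any one dimension, whatever the other dimensions or the volume do, and differs from the size measure in Section 9

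*Combined protocol and SAP*

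**What the plan says.** Sections 4.0 and 7.0 give the same definition twice. For one benign group it is "Primary outcome in nonfunctioning pituitary adenomas: 40% reduction in tumor size in any dimension"; for the other, "Primary outcome in prolactinomas: 40% reduction in tumor size in any dimension". MRI is planned at baseline, 3 months and 6 months, but these sections do not say at which scan response is judged. Size and volume are both to be calculated. Volume is used only as a secondary outcome, "d) percent reduction in tumor volume", and that list is for prolactinomas.

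Section 9.0, under the prolactinoma sample size, words the outcome differently: "The primary outcome is a reduction in maximal size of resistant tumors". It then fixes the interval: "The primary hypothesis is the change from baseline to 6 months". RECIST is named there only for stabilization: "Stabilization is defined as <20% reduction in any dimension on MRI by RECIST criteria". That line sets no limit on growth.

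The withdrawal rule appears in Section 5.0 ("tumor growth on MRI, he will be withdrawn from the study and referred for surgery") and in Section 8.0, item 3 ("tumor growth on MRI, they will be withdrawn from the study and referred for surgery"). Neither place says which dimension, what amount of change, or whether diameter or volume is meant. No section says how a patient withdrawn for growth is counted in the primary analysis.

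**The concern.** A rule that any one dimension can satisfy says nothing about the rest of the tumour. A mass that becomes shorter and wider can qualify as a response with little or no loss of volume. The rule also does not match the single size measure in Section 9.0, so two analysts following different sections could classify the same prolactinoma patient differently. For nonfunctioning adenomas there is no rival wording, and the any-dimension rule stands alone.

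The trial has no control arm, and Section 9.0 presents it as a search for enough activity to justify a larger randomized study. The responder count informs that decision, so it should mean one thing. It should also be clear in advance what happens to a patient who meets the response criterion and is judged to have growth.

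**Working it through.** **1. The plan's own figure.** Inputs from Section 9.0: null rate 0.20, alternative 0.40, one-sided exact binomial test, alpha 0.10, power above 80%, N = 24.

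- P(X ≥ 7 | n = 24, p = 0.20) = 0.189, above 0.10.
- P(X ≥ 8 | n = 24, p = 0.20) = 0.0892, within 0.10, so success needs 8 responders.
- P(X ≥ 8 | n = 24, p = 0.40) = 0.808.

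24 is the smallest n that meets both limits. The other five rows of the table (116, 88, 56, 44, 35) also reproduce. The sample size arithmetic is sound; the difficulty lies in what counts as a responder.

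**2. What a formal responder can look like.** Assumption: volume is proportional to the product of three diameters (the documents name the software but no formula). With one diameter at 0.60 of baseline and the other two each changed by a factor (1 + g):

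volume ratio = 0.60 × (1 + g)²

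| Change in each of the other two | Volume ratio | Volume change |
|---|---|---|
| 0% | 0.60 | −40% |
| +10% | 0.60 × 1.10² = 0.726 | −27% |
| +20% | 0.60 × 1.20² = 0.864 | −14% |
| +29% | 0.60 × 1.29² = 1.00 | 0% |
| +30% | 0.60 × 1.30² = 1.014 | +1% |
| −40% | 0.60³ = 0.216 | −78% |

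If only one other diameter grows, unchanged volume needs 1/0.60 − 1 = 67% growth. If no other diameter grows, volume falls by at least 40%.

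**3. Can the same scan also count as growth?** That depends on the meaning of growth, which the documents leave open.

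- *Any increase in any dimension:* yes. The +10% and +20% rows meet both rules.
- *Increase in volume:* not in those rows, nor at +29%. It needs slightly more than 29% in both other diameters, as in the +30% row.
- *Increase in maximal diameter:* it depends on which axis was longest at baseline.

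Under each reading some scan can meet both rules, but the set differs greatly in size.

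**4. Timing.** A growth withdrawal at the 3-month scan precedes the 6-month comparison and may leave no 6-month scan. At 6 months the planned treatment period is over. The first case is mainly an unstated classification of a missing outcome; the second is where two verdicts on one scan could arise.

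**5. Scale, for illustration only.** In 24 prolactinomas, 6 responders give p = 0.34, 7 give 0.19 and 8 give 0.089. Two reclassified patients would separate a result of 6 from a result of 8. Nothing in the documents indicates how many such patients to expect.

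**The case against.** The best defence has four parts.

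- **Section 9.0 already names a better measure.** For prolactinomas it uses maximal size from baseline to 6 months and plans a rank test and Hotelling's T² on that measure. If Section 9.0 governs, most of the problem goes away for that group. This stands in part: the documents do not say that it governs, the wording there carries no 40% threshold, and it does not cover nonfunctioning adenomas.
- **The withdrawal conflict rests on an undefined term.** A reader might infer that a scan with one dimension down 40% and the others up necessarily triggers withdrawal, so that the plan declares success and failure together. The documents do not support that. It is certain only if an increase in any single axis counts as growth, and neither section says so.
- **The responder count still reflects shrinkage in ordinary cases.** This stands. A reader might infer that the response rate does not measure shrinkage at all, but volume falls by at least 40% whenever no other dimension grows. The unchanged-volume case needs large opposite changes. In prolactinomas the secondary volume outcome would expose it; no such outcome is listed for nonfunctioning adenomas.
- **The 6-to-8 comparison is an assumed count.** This also stands. It applies only to the 24 prolactinomas. The 6 nonfunctioning adenomas have no sample size calculation of their own.

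**Conclusion.** The point holds as a defect of definition and should be corrected. Sections 4.0 and 7.0 allow a responder whose other dimensions have grown, Section 9.0 uses a different measure, and no text reconciles them or classifies growth withdrawals. On the product-of-diameters assumption, response covers volume changes from −78% to none, and to slightly above baseline in the extreme case. Its effect on the trial's result cannot be estimated from the documents.

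A reader might also infer that allowing any of several dimensions inflates the type I error. That would follow only if the 20% null rate described one named dimension. The documents do not say which it describes; if it already refers to any dimension, the exact alpha stays at 0.089. The malignant arm, whose primary outcome is progression free survival, is not affected.

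**What to change.** - In Sections 4.0 and 7.0, define response for both benign groups as a 40% reduction from baseline to 6 months in one named measure: the maximal diameter, taking this as what Section 9.0 means by maximal size. Use the same words in Section 9.0.
- State that a patient withdrawn for tumour growth is a non-responder in the primary analysis. This concerns classification only.
- Report percent volume change in both benign groups as a supporting analysis. It is useful because a shorter dimension can still grow while the maximal diameter falls.
- Confirm that the 20% and 40% rates behind N = 24 refer to the named measure.
- Reconcile the growth wording in Sections 5.0 and 8.0 with the response measure, so that the reader knows how the two relate. The clinical rule itself is for the investigators and is not changed here.

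The cost is a few sentences in the plan. No new scan or measurement is needed, and N = 24 stands if the two rates are confirmed. The downside is that the observed response rate may be lower than under the any-dimension rule. Further conditions on the other dimensions or on volume are debatable as part of the primary definition and fit better in a sensitivity analysis.

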Though pituitary adenomas are usually benign, some exhibit aggressive growth patterns and may invade parasellar structures, recur and progressively grow despite antitumor therapy, as well as even metastasize to intracranial and other distant sites (Blevins et al. 1998). There is no accepted definition of aggressive adenomas but are generally observed to involve massive invasion of surrounding brain and parasellar anatomy, rapid growth, and giant size. They tend to recur quickly after initial treatments, are unresponsive to therapy, difficult to cure, and some have a fatal outcome. Invasion into the cavernous sinus, skull base bone, and sphenoid sinus mucosa prevents curative surgery in these tumors (Buchfelder 2008).

Radiologic signs of invasion include: a tumor that completely encircles or extends beyond the lateral limit of the cavernous carotid artery; complete erosion of the clivus; and the presence of tumor within the sphenoid sinuses. Dural microinvasion occurs in 69 % of microadenomas and 94 % of macroadenomas (Selman et al. 1986).

The pathogenesis of pituitary carcinomas is unclear. They may arise from preexisting adenomas as shown by the fact that many carcinomas initially present as macroadenomas, demonstration of a monoclonal origin, and confirmation of the progressive accumulation of genetic alterations in the transformation from a pituitary adenoma to a carcinoma. Invasive adenomas may represent a biologically intermediate stage in tumor progression from benign to carcinoma (Amar et al. 1999). According to the 2004 WHO classification, tumors with invasive growth, elevated mitotic index, Ki-67 labeling index > 3 %, and extensive nuclear reactivity for p53 are considered "atypical" adenomas warranting closer monitoring for development of early regrowth (Al-Shraim et al. 2006).

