Figure 5: Immunofluorescent staining of giant nonfunctioning human pituitary adenomas (NFAs). A: erbB2 in breast cancer (positive control). B: Negative control for erbB2 (corticotroph tumor) C: erbB2 in giant NFA. D: EGFR in breast cancer. E: EGFR blocking peptide of breast tissue. F: EGFR in giant NFA. G: erbB3 in breast cancer. H: erbB3 blocking peptide of breast tissue. I: erbB3 in giant NFA.

[figure not shown]

Figure 6: erbB is overexpressed in human NFAs as assessed by Western blot. Positive controls for erbB2, erbB3, and EGFR: GH4 erbB2 overexpressing cells; negative controls: AtT20 cells; Tumors 1 and 2: small NFAs, Tumors 3 and 4: large NFAs

Summary:

We have demonstrated expression of EGFR and erbB2 in rat lacto-somatotroph cells, and EGF stimulation leads to increased prolactin mRNA expression. In GH4 cells which overexpress constitutively active erbB2, prolactin expression increased. Gefitinib treatment inhibits EGF induced erbB2 and EGFR in GH3 cells, and in mice implanted with GH3 cells, lead to decreased tumor volume and prolactin levels. Expression of the erbB receptors has been shown in human prolactinomas resistant to medical therapy as well as in large, invasive nonfunctioning adenomas.

Section 3.0 Trial objectives and purpose

Test the clinical effects of lapatinib for treatment of aggressive and recurrent pituitary tumors.

Hypothesis: We hypothesize that lapatinib will inhibit tumor growth and hormonal secretion in patients with pituitary tumors. Gefitinib has been approved for use in non-small-cell lung cancer but has not been proven to elicit significant tumor size reduction. Lapatinib, which inhibits both EGFR and erbB2 tyrosine kinases, has been proven to be effective in slowing disease progression in breast cancer both as monotherapy and when given in combination with capecitabine(Geyer et al. 2006). In a proof of concept clinical trial, we plan to treat patients with aggressive pituitary tumors resistant to standard therapy with lapatinib for 6 months to assess for stabilization of tumor size and pituitary tumor secretory profiles. In addition, we will treat subjects with malignant pituitary tumors which have failed to respond to other therapeutic modalities. These subjects will be in a separate arm of the study for patients with malignant pituitary tumors.

Section 4.0 Trial Design

Conduct a proof of concept single cohort open label study of lapatinib in patients with pituitary tumors.

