Will draw CBC with differential, BMP, LFTs (15 cc blood)
For those with prolactinomas, will also check PRL.
For those with acromegaly from malignant tumors, will check GH levels on 2 hour OGTT
For those with ACTH secreting malignant tumors, will check 24 hour urinary free cortisol
Do ECG
Urine Pregnancy Test
Those with pre-existing visual field compromise, visual field testing

Visit 7: time of 6 months on drug
Physical exam and history
Will draw CBC with differential, BMP, LFTs (15 cc blood)
For those with acromegaly from malignant tumors, will check GH levels on 2 hour OGTT
For those with ACTH secreting malignant tumors, will check 24 hour urinary free cortisol
Pituitary hormones as well—PRL, TSH, thyroid panel, free T4, 8 am cortisol (if indicated), IGF-1, LH, FSH, total and free testosterone for males (15 cc blood)
Tubes for lab for EGFR, her2 levels (10 cc blood)
Do ECG, Echocardiogram
Check visual fields
Dilated retinal exam
Visual acuity check
Ocular pressure check
Color Vision test
Do MRI of pituitary with and without IV gadolinium
Urine Pregnancy Test

Visit 8: time of 1 mo off drug
Physical exam and history
Will draw CBC with differential, BMP, LFTs (15 cc blood)
For those with prolactinomas, will also check PRL.
For those with acromegaly from malignant tumors, will check GH levels on 2 hour OGTT
For those with ACTH secreting malignant tumors, will check 24 hour urinary free cortisol
Draw tubes for EGFR, Her2 levels (10 cc blood)
Do ECG, Echocardiogram

Urine Pregnancy Test

Note: Study visits may be conducted over 2 days to allow for sufficient time to complete the procedures, scheduling availability, and patient preference.

Study procedure flowsheet:

(See following page)

Procedure	Baseline Visit	Visit #2 (+30 days)	Visit #3 (+60 days)	Visit #4 (+90 days)	Visit #5 (+120 days)	Visit #6 (+150 days)	Visit #7 (+180 days)	Visit #8** (+210 days)
Laboratory Blood Tests (may include levels of hormones, cholesterol, CBC, and metabolic panel)	X	X	X	X	X	X	X	X
MRI of the Pituitary	X^^			X			X	
Echocardiogram	X		X		X		X	X
Electrocardiogram (ECG)	X	X	X	X	X	X	X	X
Visual Field Test	X	X^	X^	X		X^	X	
History and Physical	X	X	X	X	X	X	X	X
Informed Consent	X							
Color Vision Test	X			X			X	
Ocular Pressure Check	X						X	
Visual Acuity	X						X	
Dilated Retinal Exam	X			X			X	
Hormonal profile	X	X	X	X	X	X	X	X
Oral Glucose Tolerance Test (OGTT) (malignant arm)	X*	X*	X*	X*	X*	X*	X*	X*

24-hour Urinary Free Cortisol (malignant arm)	X+							

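### The malignant arm's primary outcome is progression-free survival, but scheduled tumour imaging covers only the pituitary, so PFS and complete response would tend to be overstated

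*Combined protocol and SAP*

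**What the plan says.** Section 3.0 sets up the group: "These subjects will be in a separate arm of the study for patients with malignant pituitary tumors". Sections 4.0 and 7.0 give its endpoints: "Primary outcome in malignant pituitary tumors: Progression free survival", and "Secondary outcomes in malignant pituitary tumors: partial response, complete response, mortality, 24 hour urine free cortisol levels for Cushing carcinomas", followed by IGF-1 for acromegaly carcinomas.

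The imaging is described in three places:

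- **Section 6.0, Visits 4 and 7 (months 3 and 6):** "Do MRI of pituitary with and without IV gadolinium". Visit 1 has a baseline MRI, which a recent outside scan can replace.
- **Study procedure flowsheet:** the only tumour-imaging row is "MRI of the Pituitary". The malignant arm has its own rows for OGTT and urinary free cortisol, but none for imaging.
- **Section 7.0:** "MRIs will be performed at baseline and at 3 and 6 months" and "All MRIs will be centrally read by the dedicated pituitary radiologist at CSMC". These sentences stand under the nonfunctioning-adenoma outcome, but no other timing or reader is given for the malignant arm.

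Background section B4 says that some aggressive tumours may "even metastasize to intracranial and other distant sites".

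Progression, partial response and complete response are not defined for this arm. Section 9.0 gives it no sample size and no analysis. The one reference to RECIST, in Section 9.0, sits in the prolactinoma text and defines stabilization.

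**The concern.** PFS and complete response are statements about disease at every site. A site that the study never images cannot contribute study-detected radiological progression, and disappearance of disease there cannot be confirmed. A patient whose disease grows elsewhere while the pituitary tumour is stable could therefore be counted as progression-free if nothing else brought that growth to light.

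The error runs in one direction, in favour of the drug. The arm has no comparator, so nothing in the trial would expose it. Section 9.0 describes the study as a search for enough activity to justify a larger randomized trial, and an inflated PFS or complete response rate in this arm could feed into that decision.

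**Working it through.** **No figure to reproduce.** The documents give no PFS rate, event count, sample size or null value for this arm. The check is first a comparison of endpoint and schedule, then an illustration on assumed inputs.

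**Endpoint against schedule**

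| What the endpoint needs | What the plan schedules |
|---|---|
| Baseline image of each site where disease is known or suspected | Pituitary MRI only |
| Follow-up image of the same sites | Pituitary MRI at months 3 and 6 only |
| Definition of progression and response | None for this arm |
| Rule for non-imaging evidence (symptoms, hormones, unscheduled scans) | None |

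Other assessments could reveal progression elsewhere: history and physical examination at every visit, GH on OGTT in acromegaly, urinary free cortisol in ACTH-secreting tumours, and deaths. The plan does not say whether any of the clinical or hormonal findings count as progression. The hormone tests do not help in non-secreting tumours.

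**Illustration for PFS (all inputs assumed)**

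- S = true 6-month PFS
- f = share of the progression hazard that first appears outside the pituitary
- c = share of those outside events that are detected some other way

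A missed outside event leaves the patient under observation and still at risk of a detected event. The observed hazard is then the true hazard times 1 − f(1 − c), so

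observed PFS = S^(1 − f(1 − c)).

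With S = 0.40:

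| f | c | Exponent | Observed PFS |
|---|---|---|---|
| 0.20 | 0 | 0.80 | 0.40^0.80 = 48% |
| 0.50 | 0 | 0.50 | 0.40^0.50 = 63% |
| 0.20 | 0.5 | 0.90 | 0.40^0.90 = 44% |
| 0.50 | 0.5 | 0.75 | 0.40^0.75 = 50% |

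The direction does not depend on S. With f = 0.50 and c = 0, a true 30%, 50% or 70% would be read as 55%, 71% or 84%. The exponent is below 1, and the bias upward, whenever f > 0 and c < 1.

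**Illustration for complete response (assumed)**

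Suppose 20% of patients show complete response in the pituitary and 25% to 75% of them have residual disease elsewhere. True complete response is then 0.20 × 0.75 = 15% down to 0.20 × 0.25 = 5%.

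**The case against.** The strongest reply is that the text never confines progression to the pituitary scan. A reader might infer that the protocol, followed literally, scores a patient with known growing metastases as progression-free. The documents do not support that: progression is undefined, and no sentence tells anyone to disregard known disease elsewhere. The defect is lack of systematic detection, not an instruction to ignore. Examinations, hormone tests, deaths and unscheduled imaging would reveal some events, so an assumption of zero detection is an extreme.

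Three further inferences also fail.

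- **That PFS times are meaningless because progression can be dated only to month 3 or 6.** Deaths have exact dates. Sections 5.0 and 8.0 allow visual-field worsening or tumour growth on MRI to trigger withdrawal at any time. Scan-detected progression is interval-censored, which is coarse but can be analysed.
- **That a true 40% would be read as 52% to 70%.** Those values come from 1 − 0.60 × 0.80 and 1 − 0.60 × 0.50. They assume that no outside event is otherwise detected and that no such patient has pituitary progression or dies by month 6. They are an upper bound on assumed inputs.
- **That spread is usual in this group.** Section B4 says only that it can happen and gives no frequency.

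It is also fair to say that the arm has no success rule that could be wrongly met, because the 30 planned subjects are all prolactinomas or nonfunctioning adenomas. That limits the consequence to a descriptive estimate. Rarity may also excuse limited imaging.

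What survives these replies is narrower but sound. The schedule cannot support an endpoint named PFS, nor a complete response, whatever the size of the arm. Section 6.0 does continue data collection for responders who stay on the drug, but the flowsheet footnote leaves their follow-up to clinical judgement and schedules no further imaging.

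**Conclusion.** The concern holds. Progression outside the pituitary is not systematically detected, and complete response cannot be verified. PFS and complete response reported under those names would tend to be overstated.

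The size is unknown, because the documents contain no rates. The range of 44% to 63% observed against a true 40% rests on three assumptions: the true rate, a 20% to 50% share of hazard first appearing elsewhere, and detection by other means of between none and half of that share. Only the direction follows from the design, and it requires that at least some outside progression occurs and goes undetected.

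This is more than a missing definition, since defining progression would not by itself make unimaged sites observable. It should be corrected before analysis.

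**What to change.** No added scans are needed.

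1. For the whole arm, name the imaging endpoint pituitary (local) progression-free status and pituitary response. Do not report it as PFS or complete response. Use one label for every patient, because labelling according to who happened to be scanned elsewhere would mix endpoints within the arm.
2. Count as events death from any cause, growth on the study MRI, and any extra-pituitary progression documented in routine care. Known progression elsewhere is then never scored as a success. The label stays local because absence of progression is checked systematically only in the pituitary.
3. State one growth threshold. Apply it to sites that have a baseline image, and add unequivocal new lesions.
4. Report the 6-month proportion with an exact binomial interval, and state in advance how early withdrawals are counted.
5. Treat scan-detected progression times as interval-censored, and use exact dates for deaths.
6. State in the report that extra-pituitary sites were not systematically imaged.

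The cost is endpoint wording, collection of routine-care imaging reports, and a narrower and less favourable claim. Routine-care ascertainment will be uneven and partly driven by symptoms, and that must be disclosed with the result.
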